## Conclusion

In conclusion, the risk-benefit profile of ZPL-5212372 supports the continued development of this compound and confirms that there is minimal risk associated with the evaluation of this compound in an AD patient population. However, as this is the first topical administration of ZPL-5212372 the study will be conducted initially in a cohort of healthy volunteer subjects followed by an in-house cohort of patients with moderate to severe AD prior to treating a cohort of moderate to severe AD patients as out-patients.

## **2 STUDY OBJECTIVES AND ENDPOINTS**

### **2.1 Primary Objectives**

#### Cohorts 1 and 2

To assess the safety and tolerability, local and systemic, of ZPL-5212372 administered as a topical ointment (containing 1.0% (w/w) concentration of ZPL-5212372) twice daily, for 1 week, to healthy subjects and patients with moderate to severe AD.

#### Cohort 3

To evaluate the efficacy of ZPL-5212372 administered as a topical ointment (containing 1.0% (w/w) concentration of ZPL-5212372) twice daily, for 2 weeks, to patients with moderate to severe AD.

### **2.2 Secondary Objectives**

#### Cohorts 1 and 2

To investigate the systemic pharmacokinetics of ZPL-5212372 following single and multiple dose topical applications of a 1.0% (w/w) concentration of ZPL-5212372 ointment, administered twice daily, for 1 week, to healthy subjects and patients with moderate to severe AD.

#### Cohort 3

To assess the safety and tolerability, local and systemic, of ZPL-5212372 administered as a topical ointment (containing 1.0% (w/w) concentration of ZPL-5212372) twice daily, for 2 weeks, to patients with moderate to severe AD.

To investigate the trough concentrations of ZPL-5212372 in patients with moderate to severe AD following twice daily applications of ZPL-5212372 administered as a topical ointment (containing 1.0% (w/w) concentration of ZPL 5212372).

### **2.3 Exploratory Objectives**

#### Cohorts 1 to 3

To explore the subjects perception of the Ziarco development ointment formulation using the Ziarco Ointment Questionnaire.

### **2.4 Endpoints**

#### **Cohort 1 (Healthy Volunteers)**

Primary Endpoints: Safety

Adverse events, local tolerance assessments, supine vital signs (BP and pulse rate), 12-lead ECG, laboratory safety tests (clinical chemistry, haematology and urinalysis).

Secondary Endpoints: Pharmacokinetics

ZPL-5212372 plasma concentrations Day 1 (sd):  $AUC_{\tau}$ ,  $C_{max}$  and  $T_{max}$

ZPL-5212372 plasma concentrations Day 7 (ss):  $AUC_{last}$ ,  $AUC_{\tau}$ ,  $C_{max}$ ,  $T_{max}$ , and  $t_{1/2}$ .

Observed accumulation ratios based on  $AUC_{\tau}$  and  $C_{max}$

Exploratory Endpoints:

Subject responses to Ziarco Ointment Questionnaire.

**Cohort 2 (Moderate to Severe AD patients)**

Primary Endpoints: Safety

Adverse events, supine vital signs (BP and pulse rate), 12-lead ECG, laboratory safety tests (clinical chemistry, haematology and urinalysis).

Secondary Endpoints: Pharmacokinetics

ZPL-5212372 plasma concentrations Day 1 (sd):  $AUC_{\tau}$ ,  $C_{max}$  and  $T_{max}$

ZPL-5212372 plasma concentrations Day 7 (ss):  $AUC_{last}$ ,  $AUC_{\tau}$ ,  $C_{max}$ ,  $T_{max}$ , and  $t_{1/2}$ .

Observed accumulation ratios based on  $AUC_{\tau}$  and  $C_{max}$

Exploratory Endpoints:

Patient responses to Ziarco Ointment Questionnaire.

**Cohort 3 (Moderate to Severe AD patients)**

Primary Endpoints: Efficacy

Percentage change from baseline in the Eczema Area and Severity Index (EASI) score

Secondary Endpoints: Efficacy

Change from baseline in the Numerical Rating Score (NRS) for Pruritus (Worst Itch) over 24 hours

Change from baseline in the NRS for Sleep Disturbance

Change from baseline in Duration of Itching

Change from baseline in Verbal Rating Score (VRS) for Pruritus

Change from baseline in BSA

Reduction in Investigators Global Assessment (IGA) Score (subject will be deemed to have had a response with a reduction from baseline of at least 2 points)

Patient Global Impression of Change (PGIC)

#### Secondary Endpoints: Safety

Adverse events, supine vital signs (BP and pulse rate), 12-lead ECG, laboratory safety tests (clinical chemistry, haematology and urinalysis).

#### Secondary Endpoints: Pharmacokinetics

Trough Plasma ZPL-5212372 concentrations

#### Exploratory Endpoints:

Patient responses to Ziarco Ointment Questionnaire.

### **3 OVERALL DESIGN AND PLAN OF THE STUDY**

#### **3.1 Overview**

This is a randomised, adaptive design, double-blind (3rd party open), placebo controlled, sequential group study to determine the safety, tolerability, PK and efficacy of twice daily application of topical ZPL-5212372 (1.0% w/w) ointment administered for up to 2 weeks in adult healthy volunteers and in patients with moderate to severe atopic dermatitis.

This study will consist of 3 sequential cohorts each separated by formal safety reviews. The study will recruit cohorts sequentially and use sentinel subjects (n=3) in Cohorts 1 and 2 to minimize the risk to subjects and make it possible to modify specific features of the study dependent on emerging data; however the flexibility of the adaptive features will be constrained by clear boundaries/stopping criteria. The main features of each cohort are summarized in Table 1 below:

**Table 1 - Summary of cohorts with overview of study**

	Cohort 1	Cohort 2	Cohort 3
Subject Population	Healthy adults	Moderate to severe AD patients	Moderate to severe AD patients
In-patients/Out-patients	In-patients	In-patients	Out-patients
Total Number of subjects	12	12	30
Ratio Active:Placebo	2:1	2:1	2:1
Dosing Duration	7 days	7 days	14 days
Follow-up Visit (after last dose of study medication)	7-14 days	7-14 days	7-14 days

Progression from Cohort 1 to Cohort 3 will be dependent on the demonstration of adequate safety within the protocol defined boundaries. In Cohorts 1 and 2, complete data sets from a minimum of 4 active and 2 placebo subjects with 40% BSA treated with study ointment will need to be reviewed by the Safety Review Team in order to decide whether to proceed as planned to the next cohort. In the event that it is decided not to proceed to the next cohort, the reviewers may decide to modify the study within the boundaries of the adaptive features and continue, to submit a substantial protocol amendment or suspend the study. In addition,

in order to ensure subject safety, Cohorts 1 and 2 will be split to have an initial sentinel group which will precede the remaining subjects in the cohort. The sentinel group will consist of 3 subjects (2:1 Active to Placebo) and these subjects will be dosed twice daily, to cover 10% BSA with study ointments for 7 days. Provided that the study ointments are well tolerated after 48 hours (i.e. 4 applications) the remainder of the cohort (9 subjects; 2:1 Active to Placebo) may start dosing with coverage of 40% BSA BID for 7 days. All subjects in Cohorts 1 and 2 will remain in the CRU for the duration of the study. Cohort 3 will have AD affected skin dosed to a maximum of 50% BSA. A 50% BSA has been selected as the maximum BSA to be dosed to ensure that the total BSA of AD affected skin is not excessively different from the maximum area of treated skin in Cohorts 1 and 2 (40% BSA). It also accounts for the fact that AD patients total BSA will vary over time due to flare ups of the disease for a multitude of reasons which cannot be controlled within the study, including due to withdrawal from their normal medication prior to randomisation.

[figure not shown]
All subjects will have a screening visit to confirm suitability to enter the study, within 28 days of Day 1. AD patients in Cohorts 2 and 3 will be required to switch from their usual emollient to using the study emollient twice daily for at least 7 days prior to Day 1 and throughout their participation in the study. Dosing will commence on Day 1 and continue for 7 or 14 days, depending on which cohort subjects are allocated to. Subjects in Cohorts 1 and 2 will remain in the unit until Day 9 (48 hours after the last application of study ointment). Subjects in Cohort 3 will have their first application of ointment in the unit and continue dosing at home, returning to the unit for assessments on Days 5, 8, 10 and 15 (after the last ointment application at home on the evening of Day 14).

All subjects will be required to attend the CRU for a follow-up visit 7-14 days after the last application of study ointment. AD patients may recommence use with other topical or systemic treatments for their AD, if required, from either discharge from the CRU (Cohort 2) or the end of dosing (Cohort 3).

[figure not shown]
This protocol will be adaptive and designed to enable knowledge gained from the previous cohort to be applied to subsequent cohorts. Changes made will be within the boundaries of the adaptive elements with clear control mechanisms and guidance for staying within these boundaries.

A summary of the study design is shown in Figures 2-5.

[figure not shown]
**Figure 2 - Overall Study Design**

[figure not shown]
**Figure 3 - Study Design Cohort 1 (HV)**

**Figure 4 - Study Design Cohort 2 (AD Patients)**

**Figure 5 - Study Design Cohort 3 (AD Patients)**

A study schedule is provided in Tables 9-11 schedule of activities.

### 3.2 Adaptive Categories and Features

The adaptive categories and individual features of this study along with the limits (boundaries) which define the maximal risk and minimum safety requirements associated with the features are described in Tables 2 to 5 below.

**Table 2 - Investigational Medicinal Product/Dose**

Adaptive study design category	Adaptive Features	Boundaries
Dosing Regimen	
 
1. Dosing regimen may be adapted in accordance with PK, safety, tolerability - local and systemic data (as applicable) collected up to the decision making time-point.
 
2. Permissibility of dosing regimen adaption within and/or between cohorts
 
 
The term dosing regimen includes (1) the frequency of dosing, (2) the percentage BSA covered and (3) the duration of dosing.
	
 
1. Maximum starting percent BSA dosed will be 10% BSA for Cohorts 1 & 2.
 
2. Maximum total BSA dosed will be 40% BSA for Cohorts 1 & 2.
 
3. Minimum percent BSA dosed will be 10% BSA for Cohort 3.
 
4. Maximum total BSA dosed will be 50% BSA for Cohort 3.
 
5. Minimum dosing frequency will be once daily dosing.
 
6. Maximum dosing frequency will be twice daily dosing.
 
7. Maximum duration of dosing will be 14 consecutive days.
 

Study Ointment Application	
 
1. The volume of ointment applied to each subject may vary e.g. based on the condition of their skin, body size and gender.
 
2. Subjects will have the same volume of ointment applied throughout the duration of the study. Any changes to a subjects recommended volume of study ointment will be documented.
 
	
 
1. The minimum amount of study ointment to adequately and evenly cover the dosing area should be used for each subject.
 
2. The minimum volume of study ointment that can be applied for each application is approximately 0.25 mL per 2% BSA covered i.e. 1.25 mL ointment for 10% BSA coverage; 5 mL for 40% BSA coverage & 6.25 mL for 50% BSA coverage.
 
3. The maximum volume of study ointment that can be applied for each application is approximately 1 mL per 2% BSA covered i.e. 5 mL ointment for 10% BSA coverage; 20 mL for 40% BSA coverage & 25 mL for 50% BSA coverage.
 
4. For Cohorts 1 and 2 the minimum amount of study ointment should be used for the first application. If there is not enough ointment to cover the dosing area additional study ointment can be applied (up to the maximum 1 mL per 2% BSA).
 
5. For Cohort 3 the minimum amount of study ointment should be used for the first application in the CRU. If there is not enough ointment to cover the dosing area additional study ointment can be applied (up to the maximum 1 mL per 2% BSA).
 

Study Emollient Application	
 
1. Cohorts 2 and 3 only. Adaptable use of different methods of application for study ointment and study emollient
 
2. Cohort 3 only. Alternate emollients other than those defined as 'study emollients'
 
	
 
1. Use of study ointment before or after study emollient administration
 
2. Duration of time between study ointment and study emollient applications between 5 and 30 minutes.
 
3. Stop the use of study emollient on areas treated with study ointment.
 

	may be used.	
 
4. Stop the use of study emollient in the event of any hypersensitivity reactions caused by emollient.
 
5. Change the emollient used from 'study emollient' due to any potential or actual hypersensitivity reactions with the approval of the Ziarco CMO (Cohort 3 only).
 

--	--------------	--

**Table 3 - Timing/Scheduling**

Adaptive study design category	Adaptive Features	Boundaries
Visits	
 
1. The number and timing of the study in-life visits may be adjusted for Cohort 3. Excluding any unscheduled visits for subject safety.
 
	
 
1. Minimum of 3 visits (excluding unscheduled visits)
 
2. Maximum of 5 visits (excluding unscheduled visits)
 
3. Visit windows may vary by <math>\pm 1</math> day
 

	
 
2. Cohort 3 maybe subjected to short in-patient stay at beginning of treatment
 
	
 
1. Maximum of 3 days in-patient stay to mitigate any local toleration issues and ensure appropriate dosing by patients
 

**Table 4 - Study Participants**

Adaptive study design category	Adaptive Features	Boundaries
Subject number	
 
1. The number of subjects in Cohorts 1 and 2 may be decreased as there is no formal sample sizing for Cohorts 1 and 2.
 
	
 
1. Upon completion of a cohort the minimum safety data requirements for progression between cohorts is complete datasets for 4 active and 2 placebo subjects treated with 40% BSA coverage of ointments.
 
2. Minimum and maximum evaluable subjects for Cohorts 1 and 2 will be 6 and 12.
 
3. Ratio of 2 active :1 placebo will be used throughout the study.
 

**Table 5 - Assessments**

Adaptive study design category	Adaptive Features	Boundaries
Assessments	
 
1. Safety/tolerability samples and assessments (such as dermal scoring, safety laboratory, vital signs, ECG's etc).
 
	
 
1. No changes to the timing and frequency of non-safety assessments is allowed.
 
2. Timing and number of safety assessments may change based on clinical need.
 

	
 
2. PK samples: Timing and number of PK samples may change based on the emerging PK profile.
 
	
 
1. There will not be an increase in the number of PK samples taken but fewer samples may be taken.
 
2. Timing of samples may be changed dependent on the emerging plasma concentration data.
 

As the study progresses and safety, toleration and PK data become available the adaptive features of the study may need modifying to improve subject safety and reduce associated risks. Any decisions to modify any adaptive features within the boundaries described in the protocol will be documented and approved (signed) by the CMO prior to any implementation of the modifications. If the protocol requires changes which are outside the boundaries described in the protocol then a protocol amendment will be written. Any associated study documents e.g. informed consent document (ICD), will be updated and re-approved as appropriate.

### **3.3 Termination or Suspension of Study**

The study will be completed as planned unless one or more of the following criteria are satisfied that require temporary suspension or early termination of the study.

- New information or other evaluation regarding the safety or efficacy of the study medication that indicates a change in the known risk/benefit profile for the compound, such that the risk/benefit is no longer acceptable for subjects participating in the study.
- Significant violation of Good Clinical Practice (GCP) that compromises the ability to achieve the primary study objectives or compromises subject safety.

### **3.4 Termination or Suspension of Investigational Sites**

A study site may be terminated prematurely or suspended if the site (including the investigator) is found in significant violation of GCP, the protocol or the contractual agreement or is unable to ensure adequate performance of the study.

In the event that the sponsor, the IEC or regulatory authority elects to terminate or suspend the study or the participation of an investigational site, a study-specific procedure for early termination or suspension will be provided by the sponsor; the procedure will be followed by applicable investigational sites during the course of termination or study suspension.

### **3.5 Progression From Sentinel Group To Main Cohort**

Cohorts 1 and 2 both contain an initial sentinel group (n=3) who will only have 10% BSA treated with study ointment BID for 7 days. After 48 hours (i.e. 4 consecutive applications) of study dosing, if no local toleration (Cohort 1 healthy volunteers) or no persistent dermal AE's (Cohort 2 AD patients) are recorded the remaining n=9 participants in the cohort may start study treatment with 40% BSA being dosed BID for 7 days. The investigator will review all the sentinel group's blinded safety data and the investigator's findings and recommendation will be communicated to Ziarco by email. Based on the investigators findings Ziarco will, either confirm via email that the remainder of the cohort may commence dosing to 40% BSA or, if there is any concern from either the investigator or the Ziarco clinical team, a teleconference will be arranged and the data from the sentinel group will be discussed. The outcome and decision of the meeting will be documented and the minutes will be signed by both the investigator and the Ziarco CMO.

### **3.6 Safety Review Meeting**

Blinded review of subject safety data (AEs, local toleration assessments, ECGs, laboratory safety tests and vital signs) and pharmacokinetic data will be performed by the Safety Review

Team in a formal safety review meeting at the end of Cohorts 1 and 2 to identify any potential safety signals and decide whether progression of the study to the next cohort is appropriate. There will be sufficient time between cohorts to allow for a thorough review of data and decision-making. The decision will be documented.

During the study, subject safety will be assessed through physical examination, vital signs, ECGs, local toleration assessments (Cohort 1 only), safety clinical laboratory tests and adverse event monitoring.

Continuation to the next cohort will proceed unless study drug-related intolerance or AEs are identified through safety monitoring. Progression to Cohort 2 will not proceed if 5 or more Cohort 1 subjects, dosed over 40% BSA, have persistent (on at least 3 consecutive occasions) local toleration reactions of  $\geq 5$  total score in the modified Draize local toleration assessment. Progression to Cohort 3 will not proceed if 5 or more Cohort 2 AD patients, dosed over 40% BSA, report persistent (on at least 3 consecutive occasions) skin related AE's potentially linked to study ointment application as opposed to changes in their normal pattern of AD disease. This includes if a patients' AD worsens beyond tolerability.

The maximum human plasma exposure level has been set at 13550 ng.hr/mL which is the no observed effect level (NOEL) exposure in rats following subcutaneous systemic dosing ( $AUC_{0-t}$ ). Progression to the next cohort will not proceed if the mean area under the concentration-time curve ( $AUC_{\tau}$ ) PK data in the previous cohort exceeds 13550 ng.hr/mL or if any of the safety stopping criteria are met.

Further details on the operation of the Safety Review Meetings will be defined in a separate procedures document.

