Pre-clinically there were no safety pharmacology findings of clinical relevance with ZPL-5212372 and the results of genotoxicity studies indicate that ZPL-5212372 does not present a genotoxic risk to humans. In addition, ZPL-5212372 did not induce local toleration reactions *in vitro* in bovine eyes or sensitisation *in vivo* in guinea-pig skin either topically or intradermally. ZPL-5212372 was well tolerated in toxicology studies up to 2 weeks in duration in rats with once daily subcutaneous (SC) systemic administration and with twice daily topical administration to mini-pigs (0.5 mL/kg of vehicle or 0.3%, 1.0% or 3.0% (w/w) ZPL-5212372 ointment applied twice daily (BID) to 10% BSA). No safety findings were identified in either the 2 week rat SC or topical mini-pig studies, hence the NOAELs are 50 mg/kg/day and 30 mg/kg/day (3.0% w/w ZPL-5212372 ointment), respectively. In the rat following 50 mg/kg/day the Cmax plasma exposures at Day 13 were 5520 and 1740 ng/mL and the AUC0-t values were 44900 and 31200 ng.h/mL in males and females, respectively. In

the mini-pig following 30 mg/kg/day the  $C_{\max}$  plasma exposures at Day 14 were 14.2 and 44.7 ng/mL and the  $AUC_{0-t}$  values were 394 and 908 ng.h/mL in males and females, respectively.

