### 3.7 Stopping Criteria

#### 3.7.1 Cohort Stopping Criteria

Formal safety review meetings will be held following each cohort to assess the safety, toleration and pharmacokinetic data collected and decide whether to proceed to the next cohort.

- PK Stopping Criteria: Progression to the next cohort will not proceed if the mean  $AUC_{\tau}$  from existing cohort data exceeds 13550 ng.h/mL.
- Skin Toleration Stopping Criteria: Progression to Cohort 2 will not proceed if 5 or more Cohort 1 subjects, dosed over 40% BSA, have persistent (on at least 3 consecutive occasions) local toleration reactions of  $\geq 5$  total score in the Draize local toleration assessment. Progression to Cohort 3 will not proceed if 5 or more Cohort 2 AD patients, dosed over 40% BSA, report persistent (on at least 3 consecutive occasions) skin related AE's potentially linked to study ointment application as opposed to changes in their normal pattern of AD disease. This includes if a patients' AD worsens beyond tolerability.
- Safety Stopping Criteria: Dose escalation will not proceed if any of the following occur in a ZPL-5212372-treated subject:
  - Severe adverse reaction(s) indicating study drug-related intolerance.

- Clinically significant ECG abnormalities (such as arrhythmias) or effects on other vital signs indicating dose-related intolerance.
- Clinically significant laboratory abnormalities (see Appendix 1 and 2) indicating dose-related intolerance.
- Other findings that, at the joint discretion of the CMO and investigator, indicate dose escalation should be halted.

If any of the above occurs, prompt medical treatment should be provided as appropriate and adverse events promptly reported to the Sponsor via telephone or email.

After satisfactory review of the available pharmacokinetic, safety, and tolerability data progression to the next cohort will occur if the administration to the previous cohort was well tolerated. Adaptive features may be discussed and modifications made based on the safety/PK or learnings from the cohort. Any modifications within the boundaries specified in the protocol will not require a protocol amendment, but will be documented in the minutes of the safety review meeting.

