## 5.7 Administration

Subjects in Cohorts 1 and 2 will have twice daily applications of either 1.0% (w/w) ZPL-5212372 ointment or matching placebo ointment approximately 12 hours apart. The morning dose will be administered between 07:00 to 10:00 hours and the evening dose approximately 12 hours later between 19:00 – 22:00 hours. Study ointment will be dispensed from the pharmacy (one jar per subject) to clinical staff. Clinical staff will consult the subjects 'body map' to confirm whether 10 or 40% BSA will have application of ointment. For 10% BSA approximately [REDACTED] and for 40% BSA approximately [REDACTED] by clinic staff at the subject's bedside. If the initial volume of ointment is inadequate to cover the dosing area, additional ointment may be applied up to a maximum of 1 mL/2% BSA (i.e. 5 mL for 10% BSA or 20 mL for 40% BSA).

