**Day 1:** 

AUC $_{\tau}$  The area under the serum concentration versus time curve, from time 0 to 12

hours, as calculated using the linear trapezoidal method when concentrations are increasing and the logarithmic trapezoidal method when concentrations

Date: 16th March 2017

are decreasing.

Cmax Maximum observed drug concentration.

 $T_{max}$  Time of the maximum serum concentration. If the maximum value occurs at

more than one time point,  $T_{\text{max}}$  is defined as the first time point with this value.

Day 7:

AUC $_{\tau}$  The area under the serum concentration versus time curve, from time 0 to 12

hours, as calculated using the linear trapezoidal method when concentrations are increasing and the logarithmic trapezoidal method when concentrations

are decreasing.

AUClast The area under the serum concentration versus time curve, from time 0 to last

available time point (48 hours), as calculated using the linear trapezoidal method when concentrations are increasing and the logarithmic trapezoidal

method when concentrations are decreasing.

Cmax Maximum observed drug concentration.

Tmax Time of the maximum serum concentration. If the maximum value occurs at

more than one time point,  $T_{max}$  is defined as the first time point with this value.

Kel Where possible, the apparent terminal elimination phase rate constant (kel) will

be calculated by linear regression of the log-linear plasma concentration-time curve. Only those time points judged to describe the terminal log-linear decline will be used in the regression. Values for this parameter will only be reported for an individual if a minimum of 3 measurable concentration-time-points during the log-linear portion of the terminal elimination phase,

excluding Cmax, are available

t½ Apparent first-order terminal elimination half-life will be calculated as ln2/kel

RAUC $\tau$  Accumulation ratio calculated as Day 7 AUC $\tau$  / Day 1 AUC $\tau$ 

RCmax Accumulation ratio calculated as Day 7 Cmax / Day 1 Cmax

SAP Version v2.0 Page 20 of 43

Date: 16th March 2017

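### The PK progression rule tests a 12-hour human AUC against a rat AUC from once-daily dosing, so a cohort at the limit would have a daily AUC twice the number named as the cap

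*Protocol*

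**What the plan says.** Protocol 3.6 states: "The maximum human plasma exposure level has been set at 13550 ng.hr/mL". It identifies the number as the rat NOEL exposure, an AUC0-t after subcutaneous dosing. Protocol 1.5 adds that it is a mean, from 15 mg/kg/day given for 13 days. Protocol 1.3 says ZPL-5212372 was given "in rats with once daily subcutaneous (SC) systemic administration".

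The human quantity tested against it is the cohort mean AUCtau. Section 3.6 says "Progression to the next cohort will not proceed if the mean area under the concentration-time curve" exceeds 13550 ng.h/mL, and 3.7.1 repeats the criterion: "PK Stopping Criteria: Progression to the next cohort will not proceed if the mean" AUCtau is above the same figure.

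SAP 4.5 defines AUCtau, for both Day 1 and Day 7, as "The area under the serum concentration versus time curve, from time 0 to 12" hours. Protocol 5.7 sets the regimen: "Subjects in Cohorts 1 and 2 will have twice daily applications", about 12 hours apart.

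The rat t is not defined. The rule does not name the study day or the treated-area group, although the skin-toleration rules beside it are limited to subjects dosed over 40% BSA.

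**The concern.** A daily dose in the rat is matched to half a daily dose in man. Nothing in either document doubles AUCtau, uses a 24-hour AUC, or explains why a direct comparison is acceptable. A numeric stopping rule ought to enforce the cap it is built on, and this one could let a cohort through with a daily exposure above the named maximum.

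It is also the last AUC check in the study. Cohort 3 may treat up to 50% BSA for 14 days and collects trough samples only, so no observed AUC will be available there.

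Interval labels are loose elsewhere too. The inhaled-dose value of 1.32 ng.h/mL is called AUC0-last in Protocol 1.3 and AUC0-12 in Protocol 1.5. That is a further reason to ask for the rat interval in writing.

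**Working it through.** **Inputs.** Cap 13550 ng.h/mL (Protocol 3.6). Tau 12 h (SAP 4.5). Two applications a day (Protocol 5.7). Rat values at 50 mg/kg/day, males then females (Protocol 1.3): "plasma exposures at Day 13 were 5520 and 1740 ng/mL" for Cmax, and for AUC0-t "values were 44900 and 31200 ng.h/mL in males and females, respectively". Mini-pig AUC0-t 394 and 908 ng.h/mL (Protocol 1.3), mean 651 (Protocol 1.5).

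**1. The plan's figure.** 13550 cannot be rebuilt, because the male and female AUCs at 15 mg/kg/day are not given. Two checks show that it is plausible:
- The mini-pig mean is (394 + 908)/2 = 651, as stated, so the plan's mean is a male/female average.
- The rat mean at 50 mg/kg/day is (44900 + 31200)/2 = 38050. Scaled by dose, 38050 x 15/50 = 11415, the same order as 13550.

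**2. Daily human AUC at the limit.** Daily AUC = AUCtau x (1 + k), where k is the evening-to-morning AUC ratio. With k = 1 (equal intervals at steady state), 2 x 13550 = 27100 ng.h/mL, and 27100/13550 = 2.0.

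**3. Could the rat interval also be 12 h?** An AUC over t hours cannot exceed Cmax x t, so t is at least AUC/Cmax.
- Females: 31200/1740 = 17.9 h. The largest possible 12 h AUC is 12 x 1740 = 20880, below the reported 31200.
- Males: 44900/5520 = 8.1 h, which settles nothing.

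A 12 h interval is therefore impossible for the females at 50 mg/kg/day. It is unlikely at 15 mg/kg/day if the sampling schedule was the same, which is an assumption.

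**4. Matched limit for AUCtau.** Limit = 13550 x 12/t, taking average concentration as constant across the window.
- t = 24 h: 13550/2 = 6775 ng.h/mL.
- t = 17.9 h: 13550 x 12/17.93 = about 9070 ng.h/mL.

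**5. Practical weight.**
- 27100/31200 = 0.87 and 27100/38050 = 0.71, so 27100 is below the female and the mean rat exposure at the NOAEL (50 mg/kg/day). It is also below the male value of 44900.
- Protocol 1.5 expects human exposure no higher than 651, and 13550/651 = 20.8, about 21-fold below the cap.
- SAP 12 reports very low and sporadic systemic exposure at the Cohort 1 and Cohort 2 reviews.

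**The case against.** The strongest reply is that the documents do not show how far the rule is off. The cap has no per-day unit and the rat t is not stated. The interval check uses 50 mg/kg/day, while the cap comes from 15 mg/kg/day. The 12-hour definition stands in an SAP dated March 2017, after the reviews it describes. A separate procedures document, not available here, governs the safety review meetings. These points limit the precision but do not remove the mismatch. Twelve hours is the natural tau under twice-daily dosing. The procedures document is described as covering how the meetings operate, whereas the protocol itself states the unconverted criterion twice.

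Three stronger readings are tempting, and none is supported.

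- *The rat data fix the excess at about 1.5 to 2 times rat daily exposure.* The lower figure comes from females alone: 2 x 31200/(24 x 1740) = 1.49. The cap is a male/female mean. With a shared 17.9 h window, male daily AUC could reach 44900 + 6.07 x 5520 = about 78400 and female 41760, a mean of about 60080. The floor is then 2 x 38050/60080 = 1.27. If the windows differ by sex, the mean ceiling is 24 x (5520 + 1740)/2 = 87120 and the floor is 0.87. These are extreme flat-profile bounds, but so is 1.49. The upper figure assumes t of at most 24 h, yet the male mini-pig values imply at least 394/14.2 = 27.7 h for an AUC0-t in these same documents.
- *Averaging in the 10% BSA sentinels loosens the gate further.* The rule is silent on pooling, but no text prescribes it. The review requires complete 40% BSA datasets, and SAP 9.2 summarises Cohort 2 parameters by treated area and day.
- *Subjects were over-exposed.* The reported exposure points the other way. Protocol 1.5 also promises on-going monitoring against 13550, and 3.7.1 has separate clinical, ECG, laboratory and discretionary stops.

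**Conclusion.** The criterion is mis-specified as written. It compares a 12-hour AUC under twice-daily dosing with an AUC0-t from once-daily dosing and gives no conversion. At the limit, daily steady-state AUC is about 27100 ng.h/mL, 2.0 times the number named as the maximum. This assumes equal 12-hour intervals and the SAP's definition of tau. The excess over actual rat daily exposure is not determinable until the rat interval is known; all that can be said is that a 12-hour rat interval is unlikely.

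The point is minor for this trial. The limit was very unlikely to bind, and even 27100 lies below both sex-specific rat NOAEL exposures. Its main value is to stop an unconverted limit from passing into a later study, where a higher concentration, larger area or longer dosing could make it matter.

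**What to change.** State the sampling interval behind the rat AUC0-t. Then define the rule fully: do not progress if 2 x mean Day 7 AUCtau in active subjects treated over 40% BSA exceeds 13550 ng.h/mL. This is an AUCtau limit of 6775 if the rat interval is 24 h. If it is not, use the window-matched limit instead (about 9070 at 17.9 h). Doubling is needed because Day 7 has only a morning application, so an AUC observed over 24 hours on that day would miss the second dose. Naming the day and the area group also closes the smaller gap in the wording.

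Both cohort reviews are past, so the action now is one line in the study report comparing 2 x Cohort 2 Day 7 AUCtau (40% BSA) with 13550, or with its matched equivalent. The SAP already derives and summarises the parameter by treated area and day. Cohort 1 needs no recheck, since its exposure was too low and sporadic for PK parameters to be calculated. Any later protocol that reuses the limit should carry the corrected wording.

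The cost is that sentence and a slightly stricter gate in future. No new samples are needed.
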